2.12 Subject-Level Data Listings

All treated subjects will be included in listings if not stated otherwise. Data listings will include the subject number as identifier (and parameter and/or visit if available) and will be sorted by subject number (and parameter and/or visit if available). Columns that indicate the treatment group will be shown in all listings.

2.13 Changes in the Conduct of the Study or Planned Analysis

All statistical analyses will be performed according to the CSP. In case of analyses deviate from SAP, all changes will be described and justified in the CSR.

3. OVERALL STUDY INFORMATION

The following information will be analyzed descriptively and corresponding details on the subject level will be provided in data listings:

- Subject overview
- Vaccination
- Visit attendance
- Protocol deviations
- Study status (incl. drop-outs and reason)
- Screening failures

Specifications on TLFs are provided in [Section 7](#).

4. BASELINE EVALUATION

For the preliminary analysis baseline data (screening visit, VS) will be presented for the Safety and mITT population by treatment group and overall. For the final analysis all tables will be repeated for the PP population. In case populations do not differ, tabulations will not be repeated.

4.1 Data Points

The following information will be analyzed descriptively in tables and corresponding details on the subject level will be provided in data listings:

- Demographic information (age, sex, race)
- Physical examination (will be listed only)
- Vaccination history
- Virology (will be listed only)
- Medical history
- Prior and concomitant medications

Pregnancy test will be only listed in the safety section. Specifications on TLFs are provided in [Section 7](#).

4.2 Derivations and Definitions

- Medications stopped clearly prior (<) to Day 0 (Visit 1) will be considered prior medications, all other medications are considered to be concomitant. Medications with a missing or incomplete stop date where it cannot clearly be decided if the stop date was before or after Day 0 will be considered concomitant.

5. IMMUNOGENICITY ANALYSIS

The immunogenicity analysis will be performed for the mITT and PP population. All tables will be presented by treatment group and overall. Data from the early termination visit or unscheduled visits will be listed only and will not be shown in summary tables by time point.

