8.7 Early Termination Visit (ET)

Subjects who are withdrawn or wish to discontinue the study prematurely for any reason shall be asked to attend an early termination visit.

If the early termination occurs within the treatment period (at or before Visit 5), subjects shall perform all procedures as defined for Visit 5. If the early termination occurs within the follow up period (after Visit 5), subjects shall perform all procedures defined for Visit 7.

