8.8 Unscheduled Visits

Unscheduled visits can be conducted whenever deemed necessary. The extent of the examination performed at an unscheduled visit is at the discretion of the investigator. All procedures completed during an unscheduled visit should be documented in the source data and should also be entered to the electronic case report form (eCRF).

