2.8 Handling Missing Data

Generally, missing values of immunogenicity variables will not be imputed, and the analysis will be limited to observed values. For missing data in AE evaluation concerning seriousness, severity or causality a worst case approach will be applied. In case of missing assignment to solicited or unsolicited, this AE will neither be counted in tables for solicited AEs nor in tables for unsolicited AEs but in tables for all AEs.

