2.11.3 Per-Protocol (PP) Population

The per-protocol (PP) population is defined as mITT population including subjects with at least one major protocol deviation that might have an impact on the immune response, see [Section 2.9](#). The PP population is the primary population for the immunogenicity analysis and will be defined in the BDRM that is conducted before preliminary analysis.

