5.2 Derivations and Definitions

- For the preliminary analysis, only PRNT₅₀ will be analyzed included time points Visit 1 (day 0), Visit 3 (day 28) and Visit 5 (day 56). For the final analysis all immunogenicity parameters will be analyzed at all available time points except passive transfer.
- Analysis of passive transfer results are not described in this SAP.
- The primary analysis compares the PRNT₅₀ titer 28 days after last MV-CHIK vaccination between treatment groups. Therefore, titers from Day 56 in Groups A-D will be considered and the titer at Day 28 for Group E.
- Seroconversion rate for anti-Chikungunya PRNT₅₀ titers is defined as proportion of subjects achieving anti-Chikungunya PRNT₅₀ titers ≥ 10 at a certain time point.
- Seroconversion rate for Chikungunya-ELISA is defined as proportion of subjects achieving Chikungunya-ELISA titers ≥ 16 at a certain time point.
- The lower limit of quantification (LLOQ) are not known for immunogenicity parameters at SAP development and therefore the following general rules will apply:
 - In data listings, the original reported value “<LLOQ” will be displayed.

Adapted from:

STAT03_A Statistical Analysis Plan

Version 6.0, Effective Date 16-Feb-2018

Confidential and intellectual property of Assign DMB. No part of this document or its contents may be duplicated, referenced, published or otherwise disclosed in any form or by any means without prior written consent of Assign DMB.

Page 15 of 29

06CJDX

- For calculations the half of the true LLOQ value will be used for such values.

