6.3 Laboratory Parameters

Data from the early termination visit or unscheduled visits will be listed only and will not be shown in summary tables by time point. All tables will be presented by treatment group and overall. Laboratory data from scheduled visits (VS, Visit 3 and Visit 5) will be tabulated by time point. Specifications on TLFs are provided in [Section 7](#).

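### SAP 5 excludes early-termination and unscheduled immunogenicity results by visit label, with no exception for samples taken inside a scheduled visit window

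*Combined protocol and SAP*

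**What the plan says.** SAP 5 (Immunogenicity Analysis) sets the rule: "Data from the early termination visit or unscheduled visits will be listed only and will not be shown in summary tables by time point". SAP 6.3 and 6.4 repeat it for laboratory data and vital signs.

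Protocol 8.7 (Early Termination Visit) provides for such samples: "If the early termination occurs within the treatment period (at or before Visit 5), subjects shall perform all procedures as defined for Visit 5". Termination after Visit 5 triggers the Visit 7 procedures instead. Table 2 of the protocol marks PRNT50 and Chikungunya ELISA in the early-termination column. Unscheduled visits are looser: "The extent of the examination performed at an unscheduled visit is at the discretion of the investigator" (protocol 8.8).

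For the primary comparison, SAP 5.2 says that "titers from Day 56 in Groups A-D will be considered and the titer at Day 28 for Group E". SAP 2.11.3 adds: "The PP population is the primary population for the immunogenicity analysis". For missing immunogenicity values, SAP 2.8 says that "the analysis will be limited to observed values", without imputation. Protocol 8.9.2 rules out replacing subjects who withdraw after randomisation.

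Neither document has a rule that maps an early-termination or unscheduled sample to a scheduled visit by its study day.

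**The concern.** The exclusion depends on the name of the visit, not on when the blood was drawn. A Group A–D subject who had both injections and terminates on Day 51–61 gives a PRNT50 sample at the time the protocol intends for Visit 5. A subject who terminates on Day 168–196 gives one in the Visit 6 window. If either sample carries the early-termination label, it is listed but not summarised, and nothing else fills the gap.

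The values concerned come from subjects who leave early, so any omission is not a random thinning of the data. Groups have 12 subjects. Timing matters too. Under SAP 2.4, sponsor personnel and the statisticians are unblinded for the Day 56 analysis, so a later ad hoc decision on Visit 6 or Visit 7 samples would be taken with treatment known.

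**Working it through.** The plan gives no power, SD or dropout figure to reproduce; SAP 1.4 says that no formal sample size calculation was made. The check is a reading of the rules, followed by a sizing.

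**Does the rule reach in-window samples?**

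| Termination | Procedures (protocol 8.7) | Window the sample may fall in | Result affected |
|---|---|---|---|
| Groups A–D, treatment period | Visit 5 | Day 51–61 | Primary titre (Day 56) |
| Group E, treatment period | Visit 5 | Day 23–33 | Primary titre (Day 28) |
| Any group, follow-up | Visit 7 | Day 168–196 or 351–379 | Visit 6 or Visit 7 titre |

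In every row PRNT50 and ELISA are drawn, and SAP 5 makes no exception.

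**Does it reach the primary ANOVA?** SAP 5 speaks of summary tables by time point. In SAP 7.1 the primary GMT table and ANOVA are titled by reference to 28 days after the last vaccination, while the other PRNT50 tables are titled by visit. However, SAP 5.1 lists the PRNT50 GMT with its ANOVA among items analysed by visit, and SAP 5.2 takes the primary titres from Day 56 or Day 28. The natural reading is that an early-termination titre stays out. This is an inference, not a stated bar.

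**How large is the effect?** Inputs: 12 per group and 60 in total (protocol 6.3); one-way ANOVA on log10 titres with five groups and two-sided 95% intervals (SAP 2.6). The number lost is assumed to be 0–2 per group.

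One group's own GMT interval, with the pooled SD held constant, scales with 1/√n:
- one lost: √(12/11) = 1.044, about 4% wider
- two lost: √(12/10) = 1.095, about 10% wider

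For a pairwise GMT ratio, the half-width on the log10 scale is t(0.975, N−5) × SD × √(1/n1 + 1/n2). Relative to 12 v 12:
- 11 v 12 (N = 59): √[(1/11 + 1/12)/(1/12 + 1/12)] = 1.0225; with the small change in t, 1.0229, so 2.3% wider
- 10 v 12 (N = 58): √[(1/10 + 1/12)/(1/12 + 1/12)] = 1.0488; with the change in t, 1.0497, so 5.0% wider

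The SD cancels in these ratios. On the fold scale, with log10 SD assumed between 0.3 and 0.6, the 95% interval extends either side of the estimated ratio by these factors:

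| Assumed SD | 12 v 12 | 11 v 12 | 10 v 12 |
|---|---|---|---|
| 0.3 | 1.760 | 1.783 | 1.810 |
| 0.4 | 2.125 | 2.161 | 2.206 |
| 0.5 | 2.565 | 2.621 | 2.688 |
| 0.6 | 3.097 | 3.178 | 3.276 |

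Using Tukey-Kramer intervals, the relative widening is almost the same (1.0231 and 1.0501).

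**Is an in-window sample a 28-day sample?** Not exactly. Windows are counted from Visit 1, so a Visit 5 sample can fall between 51 − 33 = 18 and 61 − 23 = 38 days after the second injection. Scheduled samples carry the same tolerance, so using these windows for early-termination samples adds no laxity.

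**The case against.** The best case for leaving the plan alone is that the situation may hardly arise.

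- A subject who attends on Day 51–61 and undergoes the Visit 5 procedures may simply be entered as Visit 5. That is possible, but neither document says so. It also would not help in follow-up, where a subject leaving in the Visit 6 window performs the Visit 7 procedures.
- Many treatment-period leavers will have missed an injection, which SAP 2.9 lists as a major deviation, so they may leave the per-protocol set anyway. Subjects who are only stopped from further vaccination keep their scheduled visits (protocol 8.9.1). Both points stand and narrow the primary-endpoint case mainly to fully dosed Group A–D subjects. They do not remove it, and they do not touch the mITT results.
- Unscheduled laboratory and vital-sign data may be taken for clinical reasons, and listing them separately is defensible. This stands.

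A reader might infer more than the text supports. The rule does not bar these data from all summary tables; its wording covers tables by time point. The values are not discarded, because they remain in the listings. A reader might also expect repeat draws for failed samples to be lost. The documents describe no such draws: protocol 8.11.2 freezes two PRNT50 aliquots per visit, and protocol 12.5.3 treats sample-testing issues as possible per-protocol exclusions at particular time points.

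**Conclusion.** The concern holds for immunogenicity. SAP 5 excludes by label with no in-window exception, and a rule based on actual study day is better and costs little. Reach to the by-visit results is explicit; reach to the primary per-protocol and mITT analyses is the natural reading but not stated.

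The likely effect on precision is small: about 2.3% or 5.0% on a pairwise half-width for one or two titres lost in one arm, and possibly nothing. The count of 0–2 is an assumption. A reader might infer that the primary result is biased; early leavers are a selected group, but the documents give no basis for a direction or size of bias. The stronger reason to act is that an endpoint-data decision should be fixed before unblinding.

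Two readings underlie this. The primary population is taken as per-protocol (protocol 12.5.3, SAP 2.11.3), although SAP 7.1 labels the primary tables mITT and then repeats them for per-protocol. SAP 2.11.3 literally describes that set as including subjects with a major deviation. It is read here as excluding them, in line with protocol 12.5.3, and that wording needs its own correction.

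**What to change.** In SAP 5, add a rule: an early-termination or unscheduled PRNT50 or ELISA result is assigned to the nominal visit when its actual study day is inside the protocol window (Day 28 ±5, 56 ±5, 182 ±14, 365 ±14) and no scheduled result exists for that visit. Results outside every window stay listed only. State that titres assigned in this way enter the primary ANOVA.

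Apply the rule in mITT by allocated group, without a dosing condition. An under-dosed subject with a scheduled Visit 5 sample stays in mITT, so an early-termination sample should be treated alike. Let the deviation rules in SAP 2.9 deal with incomplete dosing for the per-protocol set. State how a Group E subject who leaves at Day 28 before the placebo injection is classified, since that subject's primary titre would already have been drawn.

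Leave unscheduled laboratory and vital-sign data as listed only. Finalise the rule before the Day 56 unblinding described in SAP 2.4. The cost is one SAP paragraph and a small amount of programming; no extra sampling is needed.

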5.1 Data Points

The following information will be analyzed by visit descriptively in tables and corresponding details on the subject level will be provided in data listings:

- GMT of anti-Chikungunya PRNT₅₀ antibody (incl. ANOVA with fixed treatment group)
- Seroconversion rate for Anti-Chikungunya PRNT₅₀ antibody
- GMT of Chikungunya-ELISA antibodies (incl. ANOVA with fixed treatment group)
- Seroconversion rate for Chikungunya-ELISA antibodies
- GMT of Measles-ELISA antibodies
- T cell results (will be listed only)
- Sampling details for PRNT₅₀, ELISA CHIK, ELISA measles; T-cells and passive transfer (will be listed only)

Specifications on TLFs are provided in [Section 7](#).

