The primary end-point of the study, which was immunogenicity on day 28 after the first vaccination, showed that a single MV-CHIK immunisation elicits functional antibodies in all treatment cohorts. The medium and high dose groups induced similar levels of neutralising antibodies, which were significantly higher than the low dose group and the Priorix® control groups. A second immunisation at one or three months interval boosted the titres in all treatment groups clearly, figure 1). The low dose group showed relatively low titres of both functional and total antibody levels. A second immunisation did boost the titres clearly, however, this dose level is not suitable for a single shot vaccine. The medium dose group elicited significantly higher titres after one or two immunisations. The highest functional and total anti-CHIKV titres were elicited in the highest dose group. The functional antibodies were persistent over the study period. Very similar results were obtained by HAI. Total antibody levels have been induced by a single immunisation and boosted by a second dose.

The Measles antibody titres as measured by ELISA were boosted in all treatment groups (MV-CHIK and Priorix[®]) after the first vaccination. No clear trend between the individual groups was visible but an increase in Measles virus dose increased the geometric mean titre (GMT). The measles ELISA titres that were induced after the first immunisation were close to the detection limit of the assay. Therefore, a not additive effect was visible after a second immunisation.

The subjects that entered the study were not pre-selected for a specifically high or low Measles antibody titre. The subjects were randomly allocated to the individual treatment cohorts. To analyse the effect of pre-existing anti-measles immunity on the immunogenicity of the MV-CHIK vaccine, we investigated if a baseline anti-measles titre would cause a difference between the PRNT₅₀ titres on day 28 after the first immunisation of all subjects in MV-CHIK dose groups (independently of their dose group). This analysis showed that subjects that had a low, medium or high measles titre at baseline were equally prone for the immunogenicity of the MV-CHIK vaccine. Thus, the pre-existing immunity to the vaccine vector did not interfere with the vaccine immunogenicity.

[figure not shown]

Figure 1: Induction of neutralising antibodies after two immunisations.

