5.2 Secondary Objectives

- To compare immunogenicity, safety and tolerability between different doses and formulations of MV-CHIK during the treatment period up to day 56
- To investigate the immunogenicity and safety of a novel liquid vaccine formulation

To cover this objective immunogenicity will be determined by means of PRNT₅₀ at the following timepoints during the treatment period: Visit 1 (day 0), Visit 3 (day 28) and Visit 5 (day 56). Solicited and unsolicited AEs will be recorded at each visit during the treatment period.

- To evaluate cellular responses induced by one or two immunisations

The cellular response will be investigated by T cell analysis of PBMCs isolated at Visit 1(day 0), Visit 2 (day 14), Visit 3 (day 28), Visit 4 (day 42) and Visit 5 (day 56)

- To evaluate the long-term immunogenicity of MV-CHIK up to one year after the first MV-CHIK treatment.

The long-term immunogenicity will be observed by means of PRNT₅₀ detecting anti-Chikungunya antibodies 6 months and one year after the first treatment with MV-CHIK (at Visit 6 and Visit 7).

- To collect human sera for future efficacy evaluation, by passive transfer of anti-Chikungunya antibodies to virus susceptible non-human primates

On study day 0 (Visit 1), day 28 (Visit 3), day 56 (Visit 5) and day 365 (Visit 7) blood samples will be collected for isolation of anti-Chikungunya antibody containing human serum.

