1.2.2 Secondary Objectives

- To compare immunogenicity, safety and tolerability between different doses and formulations of MV-CHIK during the treatment period up to day 56
- To investigate the immunogenicity and safety of a novel liquid vaccine formulation
- To evaluate cellular responses induced by one or two immunizations
- To evaluate the long-term immunogenicity of MV-CHIK up to one year after the first MV-CHIK treatment
- To collect human sera for future efficacy evaluation, by passive transfer of anti-Chikungunya antibodies to virus susceptible non-human primates

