1.3.2 Secondary Endpoints

- Rate of solicited and unsolicited adverse events (AEs) during the treatment period until day 56
- Serious adverse events during the treatment period until study day 56
- Immunogenicity on days 0, 28 (group A, B, C, and D), days 0, 56 (group E) and long-term immunogenicity on day 182 (6 Month) and 365 (12 Month), confirmed by the presence of functional antibodies as determined by the plaque reduction neutralization test (PRNT₅₀).
- Measurement of anti-Chikungunya antibodies on days 0, 28, 56, 182 and 365 determined by enzyme linked immunosorbent assay (ELISA)
- Measurement of anti-Measles antibodies on days 0, 28, 56 determined by enzyme linked immunosorbent assay (ELISA)

Adapted from:

STAT03_A Statistical Analysis Plan

Version 6.0, Effective Date 16-Feb-2018

Confidential and intellectual property of Assign DMB. No part of this document or its contents may be duplicated, referenced, published or otherwise disclosed in any form or by any means without prior written consent of Assign DMB.

Page 7 of 29

[figure not shown]
06CJDX

- Induction of Chikungunya specific immune responses on days 0, 14, 28, 42 and 56 determined by T-cell assay.
- Safety laboratory parameters (hematology, serum chemistry, coagulation, urinalysis)

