2.6 Inferential Analyses

The immunogenicity analysis will compare the functional anti-Chikungunya PRNT₅₀ antibody geometric mean titer (GMT) 28 days after the last MV-CHIK vaccination between the treatment groups. The significance level will be 0.05. All p-values will be two-sided and rounded to four decimal places.

GMTs and GMT ratios will be estimated by applying an analysis of variance (ANOVA) including the factor treatment group. This will be done using log10 transformed data and taking the anti-log of the resulting point estimates for the least squares means, least squares means differences and the corresponding 2-sided 95% Confidence Intervals (CI). P-values will also be provided to compare GMTs between treatment groups adjusted for multiple comparisons according to Tukey-Kramer.

Measles- and Chikungunya-ELISA titers as well as long-term stability of anti-Chikungunya antibodies determined by PRNT₅₀ and ELISA will be analyzed likewise.

Seroconversion rates will be compared between groups using a Fisher-Freeman-Halton test.

For the safety analysis Fisher exact tests will be provided for a comparison of AE rates between treatment groups.

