1.2.3.1-1.2.3.6	n/a	Repeat tables 2.1.1-x2.1.6 for PP population (if not the same as Safety Population)	
Immunogenicity Results			
Primary Endpoint			
1.3.1.1	2.3.1.1	GMT of anti-Chikungunya PRNT ₅₀ Antibody 28 days after last MV-CHIK vaccination (mITT Population)	
1.3.1.2	2.3.1.2	ANOVA with fixed factor treatment group for GMT of anti-Chikungunya PRNT ₅₀ Antibody 28 days after last MV-CHIK vaccination (mITT Population)	
Anti-Chikungunya PRNT₅₀ Antibody			
1.3.1.3	2.3.1.3	GMT of anti-Chikungunya PRNT ₅₀ Antibody by Visit (mITT Population)	
 • Preliminary Analysis: Visit 1, 3 and 5 • Final Analysis : All available time points
1.3.1.4	2.3.1.4	ANOVA for GMT of anti-Chikungunya PRNT ₅₀ Antibody between treatment groups by Visit (mITT Population)	
 • Preliminary Analysis: Visit 1, 3 and 5 • Final Analysis : All available time points
1.3.1.5	2.3.1.5	Seroconversion rate for Anti-Chikungunya PRNT ₅₀ Antibody by Visit (mITT Population)	
 • Preliminary Analysis: Visit 1, 3 and 5 • Final Analysis : All available time points
Chikungunya-ELISA Antibodies			
1.3.1.6	2.3.1.6	GMT of Chikungunya-ELISA Antibodies 28 days after last MV-CHIK vaccination (mITT Population)	
1.3.1.7	2.3.1.7	ANOVA for GMT of Chikungunya-ELISA Antibodies between treatment groups 28 days after last MV-CHIK vaccination (mITT Population)	
n/a	2.3.1.8	GMT of Chikungunya-ELISA Antibodies by Visit (mITT Population)	
 • All available time points
n/a	2.3.1.9	ANOVA for GMT of Chikungunya-ELISA Antibodies between treatment groups by Visit (mITT Population)	
 • All available time points
n/a	2.3.1.10	Seroconversion rate of Chikungunya-ELISA Antibodies by Visit (mITT Population)	
 • All available time points
Measles-ELISA antibodies			
n/a	2.3.1.11	GMT of Measles-ELISA Antibodies 28 days after last MV-CHIK vaccination (mITT Population)	
 • All available time points

Adapted from:

Page 21 of 29

STAT03_A Statistical Analysis Plan

Version 6.0, Effective Date 16-Feb-2018

Confidential and intellectual property of Assign DMB. No part of this document or its contents may be duplicated, referenced, published or otherwise disclosed in any form or by any means without prior written consent of Assign DMB.

06CJDX

1.3.1.1 - 1.3.1.7	1.3.2.1 - 1.3.2.11	Repeat tables for PP Population	

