1.2.7	2.2.7	Concomitant Medications (Safety Population)	Subject number, Treatment (Safety), Medication, ATC Level 2 (WHODD [Version]), ATC Level 3 (WHODD [Version]), Active Ingredients, Indication category, Indication, Dose, Dose Unit, Frequency, Route, Taken prior to study, Start date, End date, Ongoing, Ongoing at final examination
1.2.5	2.2.5	Vaccination History (Safety Population)	Subject number, Treatment (Safety), Vaccination within 3 years prior screening, Date, Vaccination/Indication, ATC Level 2 (WHODD [Version]), ATC Level 3 (WHODD [Version]),
1.2.8	2.2.8	Virology	Subject number, Treatment (Safety), Virology test, Test performed, Result, Date
Immunogenicity Analysis			
1.3.1	2.3.1	Functional Antibodies Assessment (PRNT ₅₀) (ITT Population)	Subject number, Country, Treatment group, Visit, Sample performed, Reason not performed, Sample ID, Date/Time of sample, Titer [IU/ml], Serconversion
1.3.2	2.3.2	Functional Antibodies Assessment (ELISA) (ITT Population)	Subject number, Country, Treatment group, Visit, Sample performed, Reason not performed, Sample ID, Date/Time of sample, Titer [IU/ml], Serconversion
n/a	2.3.3	Measles Antibodies Assessment (ITT Population)	Subject number, Country, Treatment group, Visit, Sample performed, Reason not performed, Sample ID, Date/Time of sample, Titer [IU/ml]

Adapted from:

Page 26 of 29

STAT03_A Statistical Analysis Plan

Version 6.0, Effective Date 16-Feb-2018

Confidential and intellectual property of Assign DMB. No part of this document or its contents may be duplicated, referenced, published or otherwise disclosed in any form or by any means without prior written consent of Assign DMB.

06CJDX

n/a	2.3.4	T-cell details (ITT Population)	Subject number, Country, Treatment group, Visit, Sample performed, Reason not performed, Sample ID, Date/Time of sample, Titer [IU/ml]
n/a	2.3.5	Serum collection for passive transfer (ITT Population)	Subject number, Country, Treatment group, Visit, Sample performed, Reason not performed, Sample ID, Date/Time of sample
Safety Analysis			
Extent of Exposure			
1.4.1	2.4.1	Extent of Exposure (Safety Population)	Subject number, Treatment (Safety), Date first vaccination, Date second vaccination, Treatment duration [days], Date informed consent, Date of last attended visit, Study duration [days]
1.4.2	2.4.2	Study Medication Details (Safety Population)	Subject number, Treatment (Safety), Visit, IMP administered, Reason IMP not administered, Date/Time, Package label barcode

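### The cellular-response objective has no prespecified T-cell summary or contrast, and the measles ANOVA and fold increase named in the methods have no planned output and no Day 0 adjustment

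*Combined protocol and SAP*

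**What the plan says.** **T cells.** Protocol 5.2 sets the secondary objective "To evaluate cellular responses induced by one or two immunisations", and SAP 1.2.2 repeats it. The matching endpoint in SAP 1.3.2 is "Induction of Chikungunya specific immune responses on days 0, 14, 28, 42 and 56 determined by T-cell assay". Under protocol 8.11.2 the assay gives a number of Chikungunya-specific T cells. The immunogenicity outputs in SAP 5.1 include "T cell results (will be listed only". SAP 7.1 contains no T-cell table; the only output is listing 2.3.4 in SAP 7.2, "T-cell details (ITT Population". SAP 2.1, however, defers T-cell and measles results to the final analysis and says they will be analysed there. SAP 5.2 says every immunogenicity parameter except passive transfer will be.

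**Measles.** The endpoint is a measurement of anti-measles antibodies on Days 0, 28 and 56; no objective names measles. Protocol 12.2 applies the PRNT method to the ELISA titres. SAP 2.6 does the same for "Measles- and Chikungunya-ELISA titers as well as long-term stability of anti-Chikungunya antibodies": an ANOVA on log10 titres with treatment group as the only factor, GMT ratios, and Tukey-Kramer p-values. SAP 5.1 attaches an ANOVA to the PRNT and Chikungunya ELISA entries but not to the measles entry. SAP 7.1 has one measles table, 2.3.1.11 (to be repeated for the PP population), titled "GMT of Measles-ELISA Antibodies 28 days after last MV-CHIK vaccination (mITT Population"; its content column says every available time point. SAP 2.5 mentions tables of GMFI, but SAP 7.1 has none for any assay.

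**The concern.** A secondary objective with its own endpoint and blood draws should lead to at least one planned summary. Followed literally, SAP 5.1 ends the cellular-response objective in a subject listing, with no summary statistic, no rule for zero or background counts, and no comparison of one with two immunisations.

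Timing makes this matter. Under SAP 2.4, the sponsor personnel and statisticians who perform and review the Day 56 analysis are unblinded at that point. SAP 2.1 expects the T-cell and measles results later. A summary or model chosen then would be chosen by people who know the treatment codes and the PRNT results.

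For measles, the method section and the output list disagree on whether a between-group comparison exists. Participants also start from different levels. Phase I volunteers were not selected on measles titre and were described as having low, medium or high baseline values, and "The Measles antibody titres as measured by ELISA were boosted in all treatment groups". A model without the Day 0 titre leaves that variation in the error term.

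**Working it through.** The documents give no power, effect size or SD for these endpoints, so there is no stated figure to reproduce. The check traces each endpoint from objective to output, then sizes the gain from baseline adjustment under stated assumptions.

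**1. T cells**
- Objective: protocol 5.2, SAP 1.2.2. Endpoint: five days, SAP 1.3.2.
- Method: none in protocol 12.2 or SAP 2.6.
- Output: a listing only (SAP 5.1, 7.2); summary tables planned: 0.
- Conflict: SAP 2.1 and 5.2 promise analysis.
- Samples: 60 subjects × 5 visits = 300. Volume: 5 × 24–30 ml = 120–150 ml per subject. Against the 895–965 ml total in protocol Table 3, 120/895 = 13% and 150/965 = 16%. At Visits 2 and 4 this is the only blood drawn.

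**2. Measles**
- Endpoint: three days, so 60 × 3 = 180 planned results.
- Method: group ANOVA with Tukey-Kramer (protocol 12.2, SAP 2.6).
- Output: one GMT table, no ANOVA table, no GMFI table.
- Table 2.3.1.11: the title implies one post-dose time point, the content column all of them. Only the second reading shows Day 0.

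**3. Precision of the measles comparison**

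From the documents: 12 per group, 5 groups, two-sided 5%, Tukey-Kramer. Assumed, not from the documents: log10 SD of 0.3 to 0.6; correlation r between Day 0 and post-dose log10 titre of 0.5 to 0.8.

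Residual variance with Day 0 as covariate is multiplied by 1 − r²:
- r = 0.5: 1 − 0.25 = 0.75, a 25% cut. √0.75 = 0.866, so the interval on the log scale is about 13% narrower.
- r = 0.8: 1 − 0.64 = 0.36, a 64% cut. √0.36 = 0.60, about 40% narrower.

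The Tukey 95% half-width for a pairwise log10 difference is (q/√2) × SD × √(2/12), with q(0.95; 5 groups, 55 df) = 3.989, so q/√2 = 2.820. At SD 0.4: 2.820 × 0.4 × 0.408 = 0.461, and 10^0.461 = 2.89. With the covariate, SD is multiplied by √(1 − r²) and the df fall to 54. The 95% limits on a GMT ratio, as a multiply/divide factor, are:

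| Assumed SD | No covariate | r = 0.5 | r = 0.8 |
|---|---|---|---|
| 0.3 | 2.22 | 1.99 | 1.61 |
| 0.4 | 2.89 | 2.51 | 1.89 |
| 0.6 | 4.91 | 3.97 | 2.60 |

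Comparing raw fold increases would gain less. Their variance relative to the post-dose titre is 2(1 − r): 1.0 at r = 0.5 and 0.4 at r = 0.8, against 0.75 and 0.36 for the covariate model. GMFI is therefore useful as a description of the rise, and the covariate model for the between-group comparison.

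**The case against.** Much can be said for the plan.

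- **The T-cell data are not lost.** They are listed by subject, visit and group, SAP 2.1 and 5.2 foresee analysis, and protocol 12.6 allows added analyses. A reader might infer that the objective cannot be answered; the documents do not support that. What is missing is a prespecified analysis. The titre column in IU/ml in listing 2.3.4 looks like template carry-over: the same listing has a country column in a single-centre trial.
- **A measles rise can be seen.** Given its content column, and SAP 5.1 and 5.2, table 2.3.1.11 should show Day 0 and post-dose GMTs with intervals. A reader going by its title alone might infer that no boost could be shown; that does not hold. A GMT by group and visit answers an endpoint worded only as measurement.
- **No document promises baseline adjustment.** Under randomisation the one-factor comparison is valid. A reader might infer that group differences would mostly reflect chance baseline imbalance, but at r = 0.5 baseline explains only 25% of the variance; more than half needs r above about 0.71.
- **A ceiling would shrink the gain.** Protocol 4.4.1 reports phase I measles titres near the detection limit and no additive effect of a second dose. It does not say which limit; an upper one is an inference. If so, the baseline/post correlation would weaken, and translating the gain into an equivalent number of subjects per arm would be unreliable.

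These points limit the measles part to reconciling the outputs and a cheap gain in precision. They do not remove the contradiction on T cells or supply the missing measles and GMFI tables.

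**Conclusion.** The point holds in this limited form. As written, the SAP gives a stated secondary objective and its five-visit endpoint no summary statistic and no one-dose versus two-dose contrast, and SAP 5.1 conflicts with SAP 2.1 and 5.2. This is the main defect, and it rests on the text alone.

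For measles, the ANOVA in protocol 12.2 and SAP 2.6 has no line in SAP 5.1 or 7.1, GMFI has no table, and table 2.3.1.11 disagrees with itself. Omitting the Day 0 titre costs precision, not validity. The cost is 25% to 64% of residual variance if r is 0.5 to 0.8, which is an assumption, and less if titres meet an assay ceiling.

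**What to change.** Make the changes before the Day 56 unblinding or, failing that, before the T-cell and measles laboratory results arrive.

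1. **T cells.** In SAP 5.1, replace the listing-only entry, and add tables to SAP 7.1 by group and visit: n, median, quartiles, and within-subject change from Day 0 with a 95% CI. State a rule for zero or background counts. Name D versus E at Days 42 and 56 as the two-dose versus one-dose contrast: the two groups share dose and formulation on Day 0, and on Day 28 D receives vaccine and E placebo. Correct the result column of listing 2.3.4.
2. **Measles.** Add to SAP 5.1 and 7.1 a model of log10 titre at Days 28 and 56 with treatment group and log10 Day 0 titre, reporting adjusted GMT ratios with Tukey-Kramer, and GMFI by group and visit. Say whether it replaces or accompanies the one-factor ANOVA of protocol 12.2. Align the title of table 2.3.1.11 with its content.
3. **Ceiling.** SAP 5.2 has a rule for values below the LLOQ and none for an upper limit. If many measles values lie at the upper limit, report that proportion and add a censored-regression sensitivity analysis.

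The cost is SAP text and a few extra tables; no new data are needed.
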